2.5 Randomisation and Blinding

This study is an open-label, randomised controlled study to assess the impact of FCM in correcting IDA compared with Venofer.

Subjects will be allocated one of the following treatments: FCM or IS. The randomisation allocation ratio will be 1:1 and the randomisation will be blocked by centre. They will be assigned to site via Interactive Response Technology system during study. Totally, there will be 600 blocks with 4 as block size (15 block per centre). The randomisation schedule was generated and maintained by Tigermed according to Tigermed SOPs.

Table 1 presents the treatment group labels and Table 2 presents the visit labels that will be used in all output.

Table 1: Study Treatments

Studied Treatment	Treatment Label
FCM	FCM
Venofer	IS

Table 2: Study Visits

Visit Number (title)	Visit Label
Visit 1 (Screening)	Screening
Visit 2 (Day 1)	Baseline
Visit 3 (Week 2)	Week 2
Visit 4 (Week 4)	Week 4
Visit 5 (Week 6)	Week 6
Visit 6 (Follow-Up, Week 8)	End of study

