2.1 Design

An efficacy study in Caucasian subjects by Evstatiev et al, 2011 [15] demonstrated that FCM administered using a simplified dosing formula (as proposed in this study) was superior to IS dosed using the Ganzoni formula (at multiple 200 mg iron doses). However, since no data are available on the use of FCM in Chinese patients, a non-inferiority design has been chosen for this study, assuming that FCM treatment is at least as good as IS in Chinese subjects. A randomised design was chosen to reduce bias in baseline differences between the treatment groups.

Due to the differences in posology between the study drug (FCM) and the comparator (IS) additional administrations may be required for subjects receiving IS. In a 65 kg subject with Hb of 9 g/dL at screening, FCM would require 2 individual doses of FCM (1,000 mg iron followed by a single dose of 500 mg iron 1 week later). However, if the same subject was randomised to receive IS, the cumulative dose required (as per label) would be 1,436 mg iron which would require 7 individual 200 mg iron doses (i.e., bi-weekly dosing) starting on Day 1.

Therefore, this study will utilise an open-label design to avoid unnecessary IV placebo injections. This reduces the burden of requiring additional subject visits to both groups (as subjects receiving IS will need more dosing visits than subjects in the FCM group) as well as removing the potential for infection and other side-effects that may result from an IV placebo injection.

IV iron products are designed to deliver, in a controlled way, iron to the body and to replenish iron stores and as a consequence increase Hb concentration. Therefore, the study primary endpoint is the percentage of subjects achieving an increase in Hb \geq 2g/dL (responders) from baseline at any time up to Week 8. Since knowledge of the study drug will not impact this objective parameter, in addition to the fact that all subjects will be receiving IV iron, the open-label design is considered to be the most appropriate design for this study.

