18. Male subjects planning to father a child within 7 days from the last study drug administration.
19. Subject has any kind of disorder that compromises the ability of the subject to give written informed consent and/or to comply with study procedures and/or other reason(s) that render subject not appropriate for study participation in the opinion of the treating physician.

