6. RANDOMISATION, BLINDING AND UNBLINDING PROCEDURES

6.1 Randomisation

An Interactive Response Technology (IRT) system will be used in the study. A separate user manual that outlines the details of IRT will be provided to the sites.

All subjects screened must be identifiable throughout the study and will be given a unique study subject number. Each site will be identified by a 3 digit number, and subject numbering will be assigned by IRT. The Investigator will maintain a list of subject numbers and subject names to enable records to be matched at a later date.

Randomisation of eligible subjects will be performed before start of treatment with study drug. Randomisation will be performed based on a pre-defined, computer generated randomisation list. The subjects will be randomised 1:1 to receive either FCM administration(s) or IS. IRT will be contacted for treatment assignment following confirmation of eligibility at the Baseline visit.

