6.2 Blinding

Due to the differences in posology between the study drug (FCM) and the comparator (IS) more injections/infusions may be required for subjects receiving IS.

Therefore, the study will utilise an open-label design to avoid unnecessary IV placebo injections/infusions. This reduces the burden of requiring additional subject visits to both groups as well as removing potential infections and other side-effects that may result from a placebo IV injection/infusion.

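### A single fixed block of 4 within each centre of an open-label trial makes up to a third of allocations certain in advance to any site that knows or infers the size, and the plan neither varies the size nor says it is withheld

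*SAP*

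**What the plan says.** SAP 2.5 sets out the scheme: "The randomisation allocation ratio will be 1:1 and the randomisation will be blocked by centre", and then "Totally, there will be 600 blocks with 4 as block size (15 block per centre"). No other block size and no other stratification factor is named. The same section confirms that treatment is not masked: "This study is an open-label, randomised controlled study to assess the impact of FCM".

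Protocol 6.1 does not give the block size. It says "Randomisation will be performed based on a pre-defined, computer generated randomisation list" and, on the order of steps, "IRT will be contacted for treatment assignment following confirmation of eligibility at the Baseline visit". Protocol 6.2 explains why there is no masking: "the study will utilise an open-label design to avoid unnecessary IV placebo injections/infusions". Protocol 2.1 defends that choice by the nature of the endpoint: "Since knowledge of the study drug will not impact this objective parameter".

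Neither document says whether sites are told the block size or kept from it.

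**The concern.** In an open-label trial a centre can keep a tally of its own allocations. With consecutive 2:2 blocks of exactly four, the tally fixes the last allocation of every block and sometimes the one before it. The interactive response system hides the list, but not what can be deduced from the tally by someone who knows the block size.

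The plan leaves some room to act on such knowledge:

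- Screening may last up to 7 days, and SAP Appendix 1 rates a longer screening period as only a minor deviation.
- About 850 subjects are to be screened for 368 randomised.
- Exclusion 19 in Protocol 5.3 allows for "other reason(s) that render subject not appropriate for study participation in the opinion of the treating physician".
- The arms differ visibly in burden: one to three dosing days with ferric carboxymaltose (FCM), against dosing three times a week and up to 11 injections with iron sucrose (IS).

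Protocol 2.1's argument from an objective endpoint, supported by the central laboratory in Protocol 9.1.3, deals with how haemoglobin is measured. It does not deal with who is enrolled into which slot. The primary analysis in SAP 4.6.1 is an unadjusted difference in proportions, so it would not correct a difference in case mix. The planning figures in Protocol 11.2 differ by underlying disease, so case mix could matter.

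**Working it through.** **Step 1. The plan's own figure.** The documents give no predictability figure. The sample size reproduces: (1.960 + 0.842)² × (2 × 0.70 × 0.30) / 0.15² = 146.5, so 147 per group; 147 / 0.80 = 183.75, so 184 per group and 368 in total. This point does not affect it.

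**Step 2. Certainty within a block of 4 (1:1, six equally likely orders).** The chance that an allocation is fully determined by the earlier ones is 0, 0, 1/3 and 1 at positions 1 to 4. Share certain = (0 + 0 + 1/3 + 1) / 4 = 33.3%. Always guessing the arm that is behind is right with chance 1/2, 2/3, 2/3 and 1, so 2.833 / 4 = 70.8%.

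**Step 3. Centre size.** 600 / 15 = 40 centres (inferred, not stated), and 368 / 40 = 9.2 subjects per centre. A centre of 9 completes two blocks and opens a third: 2 × (4/3) / 9 = 29.6%. With 32 centres of 9 and 8 of 10, the expected count is 40 × 2 × (4/3) = 106.7, and 106.7 / 368 = 29.0%. One third is the ceiling, approached if a few centres enrol most subjects.

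**Step 4. Possible shift in the primary difference.** Response rates from Protocol 11.2 and SAP 2.4: FCM 73% in inflammatory bowel disease (IBD) and 82% in heavy uterine bleeding (HUB); IS 58% in IBD and 82% in HUB, the last assumed rather than observed. Assume a 50:50 mix and that sites put HUB subjects in known FCM slots and IBD subjects in known IS slots.

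- Unsteered: FCM (73 + 82)/2 = 77.5%; IS (58 + 82)/2 = 70%; difference 7.5 points.
- All predictable slots steered: FCM 2/3 × 77.5 + 1/3 × 82 = 79.0%; IS 2/3 × 70 + 1/3 × 58 = 66.0%; difference 13.0 points.
- Bias = 13.0 − 7.5 = 5.5 points. If a tenth of those slots are steered, 0.55 points. Reversing the steering reverses the sign.

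**Step 5. What such a shift would do to the test.** Take a true difference of exactly −15 points (IS 70%, FCM 55%), 147 per arm and a normal approximation: SE = √[(0.70 × 0.30 + 0.55 × 0.45)/147] = 5.58 points. One-sided error = 1 − Φ(1.960 − bias/SE): 2.5% with no bias, about 3.1% at +0.55 points and about 16.5% at +5.5 points. This borrows the size of the shift from Step 4; the Step 4 rates themselves have FCM ahead.

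**Step 6. Effect of varying the block size.** Here the site is assumed to know the set of sizes but not their order. The varied schemes are simulated with equally likely sizes; the fixed-4 row is exact.

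| Blocks | Certain, 9 subjects | Certain, 60 slots | Best guess right, 9 subjects | Best guess right, 60 slots |
|---|---|---|---|---|
| Fixed 4 | 29.6% | 33.3% | 68.5% | 70.8% |
| Random 2, 4, 6 | 3.0% | 4.0% | 67.5% | 70.1% |
| Random 4, 6, 8 | 2.8% | 2.4% | 65.0% | 67.8% |

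**The case against.** The strongest reply is that nothing shows that sites have the block size. It appears in the SAP, not in the protocol that sites work from, and the response-system manual is not among the documents. A reader might infer that sites can in fact foresee one allocation in three; the documents do not support that. The figure is conditional and an upper limit. What remains is that the plan does not state the size is withheld. A tally that returns to level after every fourth subject also invites the inference, although two or three blocks per centre make it suggestive rather than conclusive.

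A reader might also take the bias to be 8 points, from 1/3 × (82 − 58). That applies the IS contrast between the two diseases to both arms. The documents give FCM 73% in IBD, so the FCM arm can gain only 82 − 77.5 = 4.5 points per fully steered slot, and the total is 5.5.

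Nor do the documents support the inference that the bias would favour non-inferiority. Visit burden might draw subjects who cannot attend often towards FCM, but nothing links that to better response, and nothing shows that one centre recruits both IBD and HUB subjects.

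The existing safeguards are real. Assignment follows confirmation of eligibility, and the key criteria are centrally measured laboratory values. Tables 14.1.5.2 and 14.1.6.1 will show baseline characteristics and cause of anaemia. Full steering would give about 67% HUB in one arm against 33% in the other, which would be plain to see. These tables would catch gross steering, but would neither prevent it nor reveal a subtle form.

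Finally, guessing the arm that is behind needs no knowledge of block size, and varying the sizes hardly reduces its success. That stands: the remedy removes certainty, not better-than-chance guessing.

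**Conclusion.** The point holds as a conditional, avoidable weakness in the design. If a site knows or infers the fixed size of 4, up to 33.3% of its allocations are certain before enrolment, and about 30% at the average centre size implied by the SAP. The resulting selection bias is credible but not demonstrated, and its direction is unknown. The 5.5-point figure rests on four assumptions: every predictable slot is steered, the case mix is 50:50, the planning rates apply (including an IS rate in HUB that was never observed), and the blocks are complete. At a tenth of that steering the shift is 0.55 points, small against a 15-point margin. The sample size is unaffected. The change is worth making because it removes most of the certainty at little cost.

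**What to change.** If recruitment continues, amend SAP 2.5 and the response-system specification so that all unused blocks have randomly varying sizes within centre, preferably 4, 6 and 8. State that the sizes are withheld from sites and from every document they receive. A 2, 4 and 6 mix is acceptable but does less about guessing. The list holds 600 × 4 = 2,400 slots for about 368 subjects, so most of it will never be used. The cost is regenerating that part of the list and a larger possible imbalance within a centre: at most 4 subjects with blocks up to 8 (3 with blocks up to 6), against 2 now.

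SAP 2.5 describes the schedule as already generated and SAP 4.7.1 describes adverse event collection in the past tense, so enrolment may be over. In that case the allocations cannot be changed. Record who knew the block size and when. Then use the order of randomisation within each centre to classify each allocation as predictable or not, and add a prespecified sensitivity check comparing aetiology, baseline haemoglobin and ferritin by arm in the two classes. This needs no new data, but with about 107 predictable allocations it has limited power, so finding no difference would be only partial reassurance.

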2.5.1 Interim Analysis

No interim analyses are planned.

2.6 Study endpoints

2.6.1 Primary endpoint for efficacy

Percentage of subjects achieving an increase in Hb of ≥ 2 g/dL (responders) from baseline at any time up to Week 8.

2.6.2 Secondary endpoints for efficacy

- Percentage of subjects achieving an increase in Hb ≥ 2 g/dL from baseline at Weeks 2, 4, 6 and 8.
- Change in Hb from baseline to Weeks 2, 4, 6 and 8.
- The percentage of subjects with TSAT $\geq 16\%$ and serum ferritin ≥ 100 ng/mL (for subjects with underlying inflammatory disease as determined by hsCRP levels above the normal range) or > 14 ng/mL (in subjects with no apparent underlying inflammatory disease as determined by hsCRP levels within normal range) at Weeks 2, 4, 6 and 8.
- Change in TSAT from baseline to Weeks 2, 4, 6 and 8.
- Change in serum ferritin from baseline to Weeks 2, 4, 6 and 8.

2.6.3 Endpoint for safety

- Change in laboratory parameters (haematology, clinical chemistry and iron status) from baseline over the study duration.
- Summary of all treatment emergent adverse events (TEAE): type, nature, incidence and outcome overall and by underlying disease aetiology.
- Summary of changes in vital signs from baseline to Weeks 2, 4, 6 and 8.
- Summary of changes in electrocardiogram (ECG) and physical examination (including body weight) from baseline to Week 4 (for ECG only) and Week 8.

3 ANALYSIS SETS

3.1 Safety Set

All randomised subjects who have received at least one dose of study medication will be in the Safety Set (SS). The subjects in the SS will be analysed based on the treatment that they received.

3.2 Full Analysis Set

The Full Analysis Set (FAS) consists of those subjects who satisfy the following criteria:

- Randomised to treatment
- Received at least one dose of study treatment
- Had at least 1 baseline and post-baseline efficacy parameter (Hb, Ferritin or TSAT) value

The FAS will be created in accordance with the Intent-To-Treat principles.

The subjects in the FAS will be analysed based on the treatment that they were randomised to.

3.3 Per Protocol Set

The Per-Protocol Set (PPS) is defined as all subjects in the FAS with a study drug compliance between 80 and 120% and do not have any major protocol violations ([appendix 1](#)).

The subjects in the PPS will be analysed based on the treatment that they were randomised to.

As per protocol, blood samples had to be drawn before study drug administration (when planned). All laboratory efficacy assessments (Hb, Ferritin, and TSAT) that are measured from a blood sample

taken after the study drug administration will not be considered for any efficacy analysis for both PPS and FAS. The subjects will still be in the PPS if they do not have a major protocol deviation.

For subjects who took prohibited concomitant medication, all laboratory efficacy assessments (Hb, Ferritin, and TSAT) will be censored after the prohibited medication start date for both PPS and FAS. The subjects will still be in the PPS if they do not have a major protocol deviation.

4 DESCRIPTION OF THE STATISTICAL ANALYSIS

This section describes the statistical analyses, presentation of the results, and the study endpoints/measures that will be collected and/or derived during the study at the time points specified in the Schedule of Events (see Section 2.3).

4.1 General Considerations

All confidence intervals (CI) and statistical tests will be 2-sided unless otherwise specified. P-values which are greater than or equal to 0.001, and less than or equal to 0.999, will be presented to 3 decimal places. All other p-values which are less than 0.001 will be presented as <0.001, while p-values greater than 0.999 will be presented as >0.999. Confidence intervals will be presented to 1 more decimal place than the raw data. In general, the maximum number of decimal places reported shall be four.

The software used for all summary statistics and statistical analyses will be SAS® Version 9.2 or later (SAS Institute, Inc.).

4.1.1 Standard descriptive statistics

Continuous variables

Unless specified otherwise, the following standard descriptive statistics by treatment group will be obtained for continuous variables: number, mean, standard deviation, median, quartiles (Q1, Q3), minimum, and maximum. The minimum and maximum will be reported to the same number of decimal places as the raw data recorded in the database. The Q1, Q3, mean and median will be reported to one more decimal place than the raw data recorded in the database. The SD will be reported to two more decimal places than the raw data recorded in the database. In general, the maximum number of decimal places reported shall be four for any summary statistic.

Categorical variables

Unless specified otherwise, the following standard descriptive statistics by treatment group will be presented for categorical values: total number, number of values in each class of the variable and the corresponding percentage of the total number of values available will be calculated.

4.1.2 Definition of baseline, visits and visit windows

The baseline will be defined as the last available (non-missing) value before or on the day of the first administration of study drug. Study day 1 is defined as the day of the first study drug administration. For analysis relative day, if considered date less than first study drug administration date, then analysis relative day will be considered date minus first study drug administration date, otherwise, it will be considered date minus first study drug administration date + 1.

4.1.3 Planned Assessment Windows

Table 3 describes the Planned Assessment Windows that will be used in all analyses.

Table 3: Planned Assessment Windows

Visit Label	Planned Visits (Protocol Specified)	Analysis Assessment Window	Target Day
Baseline (Day 1)	--	<=1 Day	1
Week 2	± 3 days	from Day 2 to Day 21	14
Week 4	± 3 days	from Day 22 to Day 35	28
Week 6	± 3 days	from Day 36 to day 49	42
Week 8	± 4 days	>= Day 50	56

All assessments will be re-mapped into the analysis windows. For a parameter, if several assessments fall into the same analysis window, the closest to the target day will be considered for the analysis. When there are 2 assessments closest to the target day, the latest one will be considered for the analysis.

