5.4.2 Withdrawal of Subjects from Study Visits

Subjects may voluntarily withdraw from study participation at any time without having to provide a reason. Subjects may be withdrawn because of the appearance of a new health condition which may require care or medications prohibited by the protocol, unacceptable AEs, refusal to continue treatment, or at the Investigator's discretion if it is in the subject's best interest.

If a subject withdraws from the study at any time either at his or her request or at the Investigator's discretion, the reason(s), including the primary reason for withdrawal, if provided by the subject, should be recorded. Subjects who discontinue the study prematurely should undergo all End of Study assessments, if possible.

Subjects may be withdrawn by the Investigator and their study participation discontinued prematurely for several reasons. Discontinuation from the study is **mandatory** in the following circumstances:

- The subject requires blood transfusion or ESA treatment (e.g. for excessive acute bleeding) or intake of iron preparations other than the study drug. If possible, discontinuation assessments should take place before transfusion or treatment. The reason for discontinuation and the date must be recorded on the appropriate page of the case report form (CRF). The date on which the procedure actually took place should also be recorded on the CRF.
- Surgery with expected significant blood loss.
- Development of an illness, condition, or procedural complication, which would interfere with the subject's continued participation.
- The Investigator/study physician feels it is medically in the best interest of the subject to discontinue the subject's participation in the study.
- Pregnancy (to be recorded on the specific pregnancy reporting form).

Subjects may be discontinued from the study for the following reasons (reason to be recorded on the appropriate page of the CRF):

- Subject does not comply with study procedures.

Appropriate documentation will be kept for all subjects who are enrolled into the study (i.e., who provide written informed consent). All subjects who discontinue from the study will be strongly encouraged to have all assessments for the End of Study visit (Visit 6) performed.

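### The one-Hb-per-window rule in SAP 4.1.3 has no exemption for the any-time primary endpoint, so a qualifying early-termination or unscheduled Hb can be left out of the analysis

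*SAP*

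**What the plan says.** SAP 4.1.3 introduces Table 3 as the "Planned Assessment Windows that will be used in all analyses". It adds that "All assessments will be re-mapped into the analysis windows". Selection within a window is by distance: "if several assessments fall into the same analysis window, the closest to the target day will be considered for the analysis". Ties go to the later sample: "When there are 2 assessments closest to the target day, the latest one will be considered for the analysis".

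The windows are wide. Week 2 runs "from Day 2 to Day 21" (target Day 14), Week 4 covers Days 22-35 (target 28), Week 6 covers Days 36-49 (target 42), and Week 8 is Day 50 onward (target 56).

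The primary endpoint in SAP 2.6.1 and 4.6.1 is a rise of at least 2 g/dL "from baseline at any time up to Week 8". SAP 4.6.1 gives the test, margin and interval method. It does not say which Hb values enter the responder derivation.

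More than one Hb in a window is foreseeable. Protocol 5.4.2 states: "Subjects who discontinue the study prematurely should undergo all End of Study assessments, if possible". Protocol 9.2.3 includes haematology in those assessments, and Protocol 9.2.4 has unscheduled-visit data recorded. SAP 4.1.8 plans no imputation of missing efficacy values.

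**The concern.** One value per window suits the by-visit secondary endpoints, which need a single Week 4 or Week 6 result. It does not suit an endpoint that any one qualifying Hb can satisfy.

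Take a subject with an Hb on Day 28 who leaves the study and is sampled on Day 33. Both days are in the Week 4 window. Day 28 is on target, so Day 33 is not used. If the 2 g/dL rise was first seen on Day 33, the endpoint definition makes this subject a responder and the windowing rule makes the same subject a non-responder.

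Two programmers could therefore derive different primary results from the same SAP. For a given subject, leaving out values can only move the classification from responder to non-responder. If the timing or frequency of early termination differs between arms, the loss differs too. That is plausible, because iron sucrose is given three times a week (up to 11 injections) and FCM needs one to three administrations, but the documents contain no data on it.

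**Working it through.** **1. The plan's own figures.** Inputs from SAP 2.4: 70% responders in both arms, margin 15 points, one-sided 2.5%, power 80%, drop-out 20%.

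n = (1.960 + 0.842)² × (0.70 × 0.30 + 0.70 × 0.30) / 0.15² = 7.85 × 0.42 / 0.0225 = 146.5, so 147 per group. Then 147 / 0.80 = 183.75, so 184 per group and 368 in total. Both figures reproduce.

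**2. Which early-termination (ET) samples are left out.** Inputs: the Table 3 windows, the closest-value rule and the tie rule. With scheduled visits on Days 14, 28 and 42, an ET Hb is left out on Days 15-21, 29-35 and 43-49, which is 7 + 7 + 7 = 21 days. It is kept on Days 2-13, 22-27, 36-41 and 50-55.

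**3. Share of ET values left out.** Assumptions not in the documents: the ET day is evenly spread up to Day 55, and visits fall as shown. Days that coincide with a scheduled visit are not counted. Days 15, 29 and 43 are included because the SAP counts the first dose as Day 1, which puts two full weeks later on Day 15.

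| Visit timing | ET on Days 2-55 | ET on Days 15-55 |
|---|---|---|
| Days 14, 28, 42 | 21/51 = 41% | 21/39 = 54% |
| Days 15, 29, 43 | 18/51 = 35% | 18/38 = 47% |
| Either set, spread evenly over ±3 days (simulated) | 30-31% | 40-41% |

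In the simulated rows the ET value displaces the scheduled value in a further 5-11% of cases, so a scheduled Hb is then the one lost.

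**4. Subjects with scheduled visits only.** Over all combinations of visits within ±3 days (±4 at Week 8), no two visits fell in the same window. These subjects lose nothing.

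**5. Subjects and responders affected.** If every drop-out provides an ET sample:

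- Lower: 184 × 0.20 × 0.30 = 11.0 per arm.
- Upper: 184 × 0.20 × 0.54 = 19.9 per arm.

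Assume that 5-20% of the values left out were the subject's only qualifying Hb. This input has no source in the documents.

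- Lower: 11.0 × 0.05 = 0.6 responders, or 0.6/184 = 0.3 points.
- Upper: 19.9 × 0.20 = 4.0 responders, or 4.0/184 = 2.2 points.

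**6. Effect on the comparison.** An equal loss in both arms leaves the expected difference at zero. The extreme case is a loss L in the FCM arm only:

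Power = Φ[(0.15 − L) / √((0.70 × 0.30 + (0.70 − L)(0.30 + L)) / n) − 1.960]

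| L | n = 147 | n = 184 |
|---|---|---|
| 0 | 80.1% | 88.1% |
| 0.5 points | 77.2% | 85.7% |
| 2 points | 67.4% | 76.9% |

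This uses the simple normal approximation, not the SAP's continuity-corrected Newcombe interval. The n = 184 column is the ceiling for the FAS.

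**The case against.** **The primary analysis set may exclude most of these subjects.** The primary analysis is on the PPS. SAP Appendix 1 rates a visit not done as major, and likewise a missing haematology assessment at Visits 2 to 6. SAP 3.3 removes subjects with major violations. The 147 per group is also what remains after the 20% drop-out. This largely stands, and it is why the effect falls mainly on the FAS. It is not complete: the SAP does not say whether visits after withdrawal count as not done, and SAP 4.5 has detailed rules under which withdrawn subjects can be compliant, which suggests that some may stay in the PPS. SAP 4.6.1 also applies the non-inferiority test to the FAS.

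**The size rests on assumptions.** A reader might infer that the plan discards about half of all early-termination Hb values, some 19 subjects per arm. The documents do not support that as a finding. It needs even withdrawal starting only at Day 15, visits on or near target, and a sample from every drop-out, while Protocol 5.4.2 asks for one only where possible. Some mandatory reasons for leaving, such as transfusion or surgery with blood loss, make a new 2 g/dL rise less likely. SAP 3.3 already censors Hb after prohibited medication. With visits on target, each value left out is also within 7 days of a retained one.

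**One value per window equalises opportunity.** It gives each subject at most four post-baseline chances to respond, whereas counting unscheduled draws in an open-label trial could give unequal numbers. This is a fair point and should be weighed in the fix. It does not reconcile the rule with the endpoint definition.

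**Conclusion.** The conflict is real on the text. SAP 4.1.3 covers all analyses and all assessments, the primary endpoint is satisfied by any qualifying Hb, and nothing exempts it. Read literally, the rule can misclassify a responder.

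The likely size is modest: about 1-4 responders per arm, at most about 2 points. That range rests on the 20% drop-out, even withdrawal up to Day 55, a sample from every drop-out, and the unsupported 5-20% input. A different withdrawal pattern would change it.

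A reader might go further and infer that the primary non-inferiority result is biased between arms. The documents do not show this. They give no evidence of different drop-out timing, an equal loss leaves the expected difference unchanged, and the PPS may exclude most of the affected subjects. The values are also not erased: they are left out of the analysis and still appear in the listings.

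The SAP should be amended, because the point concerns the primary derivation and costs little to settle. The design does not need to change.

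**What to change.** Add to SAP 4.6.1:

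> For the primary endpoint, a subject is a responder if any post-baseline Hb (scheduled, unscheduled or early termination) up to and including the Week 8 / End of Study assessment, and not excluded under Section 3.3, is at least 2 g/dL above baseline. The closest-to-target rule in Section 4.1.3 applies only to by-visit analyses.

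The reference to Section 3.3 keeps out samples taken after dosing and values after prohibited medication. Naming the assessment avoids an ambiguity in Table 3, which gives Week 8 both as ±4 days and as Day 50 onward with no upper limit. It also avoids dropping late Week 8 values that the present rule counts.

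The SAP should state at the same time whether visits after withdrawal count as not done when PPS membership is decided.

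The cost is a short SAP addition and a small change in the derivation. Sample size, margin and conduct are unaffected. The downside is that unscheduled draws in an open-label trial can give subjects unequal numbers of chances to respond. A supportive analysis using only scheduled and early-termination values would show whether this matters.
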